## 8.4 Response Assessment Criteria

During the Treatment Phase patients will be assessed for response according to the following criteria:

Complete remission (CR) a	Bone marrow blasts <5%; absence of blasts with Auer rods; absence of extramedullary disease; absolute neutrophil count $\geq 1.0 \times 10^9/L$ (1000/ $\mu$ L); platelet count $\geq 100 \times 10^9/L$ (100,000/ $\mu$ L); independence from red cell transfusions
CR with incomplete recovery (CRI) b	All CR criteria except for residual neutropenia ( $< 1.0 \times 10^9/L$ [1000/ $\mu$ L]) or thrombocytopenia ( $< 100 \times 10^9/L$ [100,000/ $\mu$ L])
Best Response	See Section 8.4.1
Treatment failure	
Persistent Disease (PD)	Failure to achieve CR or CRI; only includes patients surviving $\geq 7$ days following completion of initial treatment, with evidence of persistent leukemia (blasts in peripheral blood, extramedullary leukemia, or persistence in the bone marrow)
Death in aplasia	Deaths occurring $\geq 7$ days following completion of initial treatment while cytopenic; with an aplastic or hypoplastic bone marrow obtained within 7 days of death, without evidence of persistent leukemia
Death from indeterminate cause	Deaths occurring before completion of therapy, or $< 7$ days following its completion; or deaths occurring $\geq 7$ days following completion of initial therapy with no blasts in the blood, but no bone marrow examination available at recovery
Relapse c	Bone marrow blasts $\geq 5\%$ ; or reappearance of blasts in the blood after achievement of a CR or CRI; or development of extramedullary disease

aBone marrow assessment REQUIRED to confirm CR. All criteria need to be fulfilled; marrow evaluation should be based on a count of 200 nucleated cells in an aspirate with spicules; if ambiguous, consider repeat exam after 5 to 7 days; flow cytometric evaluation may help to distinguish between persistent leukemia and regenerating normal marrow; a marrow biopsy should be performed in cases of dry tap, or if no spicules are obtained; no minimum duration of response required.

bBone marrow assessment REQUIRED to confirm CRI. Some patients may not achieve complete hematologic recovery prior to initiation of consolidation. CRI cannot be declared earlier than Day 35 to allow adequate time for documentation of peripheral blood recovery. Consolidation may begin no earlier than 35 days after the last induction course.

cIn cases with low blast percentages (5-10%), a repeat marrow should be performed to confirm relapse. Appearance of new dysplastic changes should be closely monitored for emerging relapse. In a patient who has been recently treated, dysplasia or a transient increase in blasts may reflect a chemotherapy effect and recovery of hematopoiesis.

A subject who is alive in a state of aplasia with no evidence of continued disease will be considered as having “no response.”

The response of patients with no post-baseline bone marrow assessment will be entered as not done.

#### 8.4.1 Best Response

Patients who complete the induction(s) with a response of CRp or CRi may be upgraded to CR during or after consolidation if the patient's peripheral blood counts meet the criteria for CR (ANC $\geq$ 1000/ $\mu$ L and Platelets  $\geq$ 100,000/ $\mu$ L). To upgrade a response to CR after peripheral blood count recovery, a new bone marrow assessment must be performed within 14 days of documented peripheral blood count recovery.

### 8.5 Remission Duration

Only patients achieving CR or CRp or CRi are assessed for remission duration. Remission duration is measured from the date of achievement of a remission until the date of relapse or death from any cause; patients not known to have relapsed or died at last follow-up will be censored on the date of their last tumor assessment.

### 8.6 Morphologic Leukemia-free State

All registered patients that have at least one evaluable post-registration bone marrow assessment performed on or after Day 14 after the last induction will be assessed for morphologic leukemia-free state. Morphologic leukemia-free state is defined as bone marrow blasts <5% AND absence of Auer rods and/or extramedullary disease.

### 8.7 Stem Cell Transplant

The number and percentage of patients transferred for stem cell transplant will be summarized.

## 9 Assessment of Safety

### 9.1 Safety Population

All patients who receive at least one dose of study drug will be considered evaluable for safety.

### 9.2 Adverse Events

#### 9.2.1 Definition of an Adverse Event

An adverse event is any untoward medical occurrence in a patient or clinical investigation subject administered with a pharmaceutical product and which does not necessarily have to have a causal relationship with this treatment. An adverse event can therefore be any unfavorable and unintended sign (including an abnormal laboratory finding, for example), symptom, or disease temporally associated with the use of a medicinal product, whether or not considered related to the medicinal product. This includes worsening of a pre-existing condition or increase in frequency of a pre-existing condition. An adverse event is considered serious if it meets any of the serious criteria listed in Section 9.2.2. To ensure no confusion or misunderstanding of the difference between the terms "serious" and "severe", which are not synonymous, the following clarification is provided:

The term “severe” is often used to describe the intensity (severity) of a specific event (as in mild, moderate, or severe myocardial infarction); the event itself, however, may be of relatively minor medical significance (such as severe headache). This is not the same as “serious”, which is based on patient/event outcome or action criteria usually associated with events that pose a threat to a patient’s life or functioning. Seriousness (not severity) serves as a guide for defining regulatory reporting obligations.

Adverse events are to be recorded in the case report form from the start of the infusion on Day 1 to the last day of the treatment period, 30 days after the last dose, with the exception of serious adverse events. (See Section 9.2.2).

Adverse drug reactions (ADRs) are all noxious and unintended responses to a medicinal product related to any dose that a causal relationship between the medicinal product and an adverse event is at least a reasonable possibility, i.e., the relationship cannot be ruled out. An unexpected ADR is any adverse reaction not identified in nature or intensity in the current Investigator’s Brochure.

#### *9.2.2 Definition of a Serious Adverse Event*

A serious adverse event (SAE) is any adverse event that:

Results in death (grade 5)

Is life-threatening

Requires inpatient hospitalization or prolongation of existing hospitalization

Results in persistent or significant disability or incapacity

Is a congenital anomaly/birth defect

These events are to be reported as serious from the start of the infusion on Day 1 to 30 days after completion of the treatment period. Medical and scientific judgment should be exercised in deciding whether expedited reporting is appropriate in other situations such as important medical events that may not be immediately life-threatening or result in death or hospitalization but may jeopardize the patient or may require intervention to prevent one of the events listed above.

#### *9.2.3 Serious Adverse Event Reporting Instructions*

The investigator must complete the Serious Adverse Event Report Form in English, assess the relationship to study treatment and send the completed form by fax within 24 hours to the Sponsor or its designee. The original and the duplicate copies of the Serious Adverse Event Form, and the fax confirmation sheet must be kept with the case report forms at the study site.

Follow-up information should be sent to the Sponsor or its designee via the original Serious Adverse Event Form, re-stating the date of the original report. Either a new Serious Adverse Event Form should be sent (stating that this is a follow-up), or the original one resent (with the new information highlighted and a new date provided). The follow-up should describe whether the event has resolved or continues, if and how it was treated,

whether the patient continued or discontinued study participation. The form and fax confirmation sheet must be retained.

The telephone and fax numbers of the local Clinical Research contact person and the contact person in the local department of Clinical Safety, specific to the site, must be listed in the investigator folder provided for each individual site and provided to the Sponsor or its designee at the start of the trial. Questions referring to a specific serious adverse event occurring in a study patient should be directed to the local Clinical Research contact person specified in the investigator folder provided for the site.

#### *9.2.4 Reporting Serious Adverse Events to Regulatory Agencies and Review Boards*

All SAEs must be reported to Jazz Pharmaceuticals, Inc. within 24 hrs of awareness, irrespective of relatedness, causality, expectedness. The WCM research team will complete and submit the US-FDA Form 3500A (MedWatch form) to [[contact]](mailto:[contact]) within 1 business day of the awareness of the SAE.

All AEs and SAEs will be reported to the WCM IRB per the policies outlined below:

All SAEs will be reported with an SAE cover sheet that documents relatedness, expectedness, and risk determination. SAE reports will be saved in the study's regulatory binder. SAE reports will be compiled to complete the Data and Safety Monitoring Board (DSMB) periodic report.

The WCM IRB must be notified within 7 calendar days of investigator notification of an SAE when all of the following conditions are met, as determined by the Principal Investigator. These SAEs are considered "immediately reportable":

- a. The event is unexpected – when its specificity and severity are not accurately reflected in the WCM consent document, Investigators Brochure, or package insert; AND
- b. The harm is "related" or "possibly related" – where there is a reasonable possibility that the harm may have been caused by the research procedure(s), or interventions; AND
- c. The harm suggests that the research places WCM subjects at greater risk of harm (including physical, psychological, economic or social harm) than was previously known or recognized.

For events that are considered immediately reportable to the WCM IRB, the SAE report must be emailed to [[contact]](mailto:[contact]).

AEs grade 3 or higher and all SAEs will be listed on the Adverse Event & IND Safety Reporting Cumulative Table and reported to the WCM IRB at the time of continuing renewal.

All AEs that are serious, unexpected and associated with the use of CPX-351 will be reported to the applicable regulatory authority (FDA in the US and to Health Canada in Canada). The period we have to report the SAE to the FDA depends on the severity of the SAE, as follows:

- **Within 7 days** of becoming aware of the SAE for fatal (Grade 5), life-threatening (Grade 4) events
- **Within 15 days** of becoming aware of all other qualifying SAEs (i.e., hospitalizations, second cancers, etc.)

### **9.3 Cardiac Toxicity Monitoring**

As anthracyclines are known to have an adverse effect on cardiac function, each patient's cardiac function will be monitored through the treatment and follow-up phases and LVEF below 50% will be recorded as an adverse event. Any decrease in LVEF >10% resulting in a nadir LVEF <50% will be reported as an SAE.

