## 6.4 Evaluation during Follow-up Phase

The following evaluations are completed during the follow-up phase:

Procedure	Evaluation	Timing
Patient status report	Survival status	Once monthly until 1 year from first treatment. After the first year record only the date of death or alive at Year 5 (Day 1825).
	Relapse status New anti-leukemic therapies	Once monthly until 1 year from first treatment. After the first year record only the date of relapse and any new leukemic therapies.
Hematology	Hemoglobin White Blood Count Platelets Differential Count	Once monthly until 1 year from first treatment. After the first year record only the date of relapse and any new leukemic therapies.
Bone Marrow Evaluation	Morphology	For patients in CR or CRi perform at any time that there is a suspicion of relapse . Following the first year of follow up, record relapse information, including any bone marrow evaluations. Not required following relapse.
Diagnostic Imaging	Echocardiography, MUGA or cardiac MRI	If last treatment phase LVEF was reduced >10% from baseline and is less than 50% repeat every 3 months until LVEF returns to baseline $\pm$ 5% or until 1 year from first treatment. Persistent reductions in LVEF of >10% with nadir values below 50% documented at 1 year are considered permanent sequelae.
Biochemistry	BUN Creatinine Electrolytes (Sodium, Potassium, Chloride) Bilirubin Alkaline phosphatase AST or ALT Protein Calcium Albumin Glucose	Perform monthly only if abnormality(ies) persists at the end of the Treatment Phase. Perform until abnormality(ies) returns to baseline, until 1 year from first treatment or the initiation of new therapy and/or relapse. (whichever is earliest)
Adverse Events/Toxicity	CTCAE v.4 assessment	Assess AEs that were ongoing at the time of discontinuation. Do NOT record any new AEs. AEs that persist without evidence of recovery for >30 days are considered permanent sequelae and do not require further follow-up.

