Day 150 or 45 Days after the last treatment whichever is later

See Section 9.3, Repeat ECHO/MUGA/cardiac MRI before the second consolidation

ECG will be performed pre-dose for each course of treatment, and at the end of each course or EOT.

Blessed, MOCA and FACT-Leu can be administered +/- 3 days from indicated day

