## 15 APPENDIX 2: Patient Evaluation Flow Sheet –Follow-up

		Monthly for 1 Year (±10 Days)	Once Years 2-5	Early Termination
Patient status report		x	x	x
Hematology		x	x	x
Biochemistry		Perform monthly only if abnormality(ies) persists at the end of the Treatment Phase. Perform until abnormality(ies) returns to baseline, until 1 year from registration, or the initiation of new therapy and/or relapse. (whichever is earliest)		
Bone Aspiration/Biopsy	Marrow	For patients in CR or CRI perform at any time that there is a suspicion of relapse. For patients in CR, perform if peripheral blood counts fall below 1000/ $\mu$ L for ANC or 100,000/ $\mu$ L for platelets for >1 month or at any time there is suspicion of relapse. For patients in CRI perform if counts fall significantly below peak recovery levels. If the peripheral blood counts in a patient with a CRI recover to CR levels ( $\geq$ 1000/ $\mu$ L for ANC or $\geq$ 100,000/ $\mu$ L for platelets), perform a bone marrow evaluation within 14 days to confirm CR. Following the first year of follow up, record relapse information, including any bone marrow evaluations. Not required following the initiation of new therapy and/or relapse.		
Echocardiography, MUGA or Cardiac MRI		If last LVEF treatment phase or Day 150 was reduced >10% from baseline and is less than 50% repeat every 3 months until LVEF returns to baseline ( $\pm$ 5%) or until 1 year from registration. Persistent reductions in LVEF of >10% with nadir values below 50% documented at 1 year are considered permanent sequelae.		
Adverse Events/Toxicity		Assess AEs that were ongoing at the time of discontinuation. Do NOT record any new AEs. AEs that persist without evidence of recovery for >30 days are considered permanent sequelae and do not require further follow-up.		

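### Section 9.3 makes LVEF falls in follow-up AEs or SAEs, but the follow-up rules give a fall first seen there no consistent route into the cardiac AE data

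*Combined protocol and SAP*

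**What the plan says.** **The commitment.** Section 9.3, citing the known cardiac effect of anthracyclines, says that each patient's "cardiac function will be monitored through the treatment and follow-up phases and LVEF below 50% will be recorded as an adverse event". It adds: "Any decrease in LVEF >10% resulting in a nadir LVEF <50% will be reported as an SAE". Neither sentence has a time limit.

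**Follow-up imaging.** Section 6.4: "If last treatment phase LVEF was reduced >10% from baseline and is less than 50% repeat every 3 months until LVEF returns to baseline" within a margin, or until one year. Appendix 2 has the same two-part condition with one more qualifying scan: "If last LVEF treatment phase or Day 150 was reduced >10% from baseline and is less than 50% repeat every 3 months".

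**Follow-up recording.** The adverse event rows of Section 6.4 and Appendix 2 both say "Do NOT record any new AEs". Neither makes an exception for cardiac findings.

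**Recording windows.** Section 4.6 stops AE collection at transplant, at any non-protocol AML treatment, or 30 days after the last dose, whichever is first. Section 9.2.1 records AEs "to the last day of the treatment period, 30 days after the last dose, with the exception of serious adverse events". Section 9.2.2 takes SAEs to 30 days beyond the treatment period, and the AE row of Section 6.2 uses the same end point for AEs. Section 6.3 takes new SAEs for up to 30 days after discontinuation.

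**Analysis.** The synopsis lists cardiac AEs (all grades, and Grades 3-5) and LVEF change before and after treatment as safety variables.

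**The concern.** Section 9.3 leads a reader to expect two things in follow-up: that every patient's cardiac function is checked, and that a qualifying fall is recorded whenever it is found. The operational sections provide neither. Scheduled follow-up scans go only to patients already known to have a qualifying fall. A qualifying fall found in anyone else, for example on a scan done for clinical reasons, meets an instruction not to record it.

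At stake is what the cardiac AE rate means. A low rate would partly reflect when recording stopped, while 9.3 would let it be read as covering follow-up of up to five years. Two people applying the text could also handle the same scan differently, one following 9.3 and the other following 6.4. Findings left off the CRF during follow-up may not be recoverable later.

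**Working it through.** The plan states no figure on this point, so the check is mainly a comparison of sections.

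**1. Can a scheduled follow-up scan find a first case?** The re-scan condition is a fall of more than 10% from baseline and an LVEF under 50%. That is the SAE definition in 9.3. Anyone who qualifies for re-scanning is already a case, so the scheduled scans can only follow recovery. Two groups get no further scheduled scan:
- patients whose last scan was normal;
- patients under 50% after a smaller fall. For example, 52% to 48% is 4 points, or 4/52 = 7.7% in relative terms. It is an AE under 9.3 but does not trigger re-scanning, whether the 10% is read as points or as relative change.

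**2. When does recording stop?** Take a patient whose last dose is on Day 5 (one induction). Section 9.2.1 ends the treatment period 30 days after the last dose. A broader reading runs the treatment period to the Day 150 visit, because Appendix 1 puts that visit on the Treatment Phase sheet.

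| Section | Rule applies to | Last recording day |
|---|---|---|
| 4.6 | AEs | 5 + 30 = Day 35, or earlier |
| 9.2.1 | AEs, SAEs excepted | Day 35 |
| 6.2 | AEs | 35 + 30 = Day 65; broad reading 150 + 30 = Day 180 |
| 9.2.2 | SAEs | Day 65; broad reading Day 180 |
| 6.3 | new SAEs | discontinuation + 30 days |
| 6.4, Appendix 2 | new AEs in follow-up | none recorded |

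These rules do not agree with one another, and none mentions LVEF.

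**3. The Day 150 scan.** Appendix 2 confirms that a Day 150 LVEF is intended, and Appendix 1 has the column (±10 days). Sections 6.2 to 6.4 do not list it. With D the day of the last dose, a scan on nominal Day 150 is 150 − D days after it:
- D = 5: 145 days, which is outside both a 30-day and a 60-day window and inside the broad reading;
- D = 90: 60 days, the edge of the 60-day window obtained by reading 9.2.1 with 9.2.2;
- D = 120: 30 days, the edge of the 30-day window.

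Whether a fall seen on that scan is recorded therefore depends on the patient's course and on which section is followed.

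**4. Scale.** Assume exponential survival with the Section 11.2 medians (m = 10 and 16 months), 30 patients, no other loss and a five-year cap. Day 150 is 4.93 months.
- Alive at Day 150: 30 × 0.5^(4.93/10) = 21.3 and 30 × 0.5^(4.93/16) = 24.2.
- Share of person-months after Day 150: 300.8/426.0 = 71% and 507.9/641.0 = 79%.
- Weight of one event: 1/30 = 3.3 percentage points.
- Illustration only: if 5% to 15% of those alive had a first late fall (an assumed range), that is 0.05 × 21.3 = 1.1 to 0.15 × 24.2 = 3.6 events. Most would not be scanned under the present schedule, so a change in recording alone would recover fewer.

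**The case against.** **The analysis is already bounded.** LVEF change is defined before and after treatment, the 30-day limit on AEs is stated openly, and no late-cardiotoxicity rate is planned. This stands in part: no planned table is computed wrongly. It does not explain why 9.3 extends monitoring and AE recording into follow-up.

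**Section 9.3 may be a specific exception to a general rule.** It has no time limit and concerns LVEF alone, so it could be read as overriding the follow-up rows. No section says so, and the follow-up rows are unqualified.

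**Recording late events could mix unlike things.** Some would come from scans without a common schedule, and some would follow transplant or salvage therapy, where Section 4.6 stops collection on purpose. This stands, and the fix has to separate them.

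**Stronger readings that the documents do not support.**
- A reader might infer that late cardiotoxicity cannot enter the cardiac AE rate at all. That is too absolute. Section 9.3 could be followed over 6.4, and a fall at the Day 150 scan could be recorded under the broader windows or appear in the LVEF-change summary.
- A reader might take the Appendix 1 footnote "Day 150 or 45 Days after the last treatment whichever is later" as timing the Day 150 echocardiogram, and so find at least 45 − 30 = 15 days between the close of the AE window and the scan for everyone. In the text available, that footnote's marker is on the response assessment row, while the Day 150 column carries a different footnote and ±10 days. The table is also visibly disordered by extraction. The footnote cannot carry a minimum gap.
- A reader might infer that ascertainment switches from all patients to known cases about 30 days after the last dose. The Day 150 scan is not restricted to known cases and is on the Treatment Phase sheet, whereas the bar on new AEs is in the follow-up tables.

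**Conclusion.** The conflict is real and is in current text. For a fall first seen in the follow-up phase, 9.3 requires recording while 6.4, Appendix 2 and 4.6 exclude it, and scheduled follow-up imaging is confined to known cases. For a fall seen at Day 150 the position is ambiguous rather than excluded.

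The effect on the cardiac AE rate cannot be sized from the documents, because they give no late-event rate. What can be said is that each event is worth 3.3 percentage points with 30 patients and that, under the exponential assumption, some 71% to 79% of five-year person-time lies after Day 150. The person-time figure measures exposure; it does not estimate missed events.

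Overall survival, 30-day mortality, the power statement and the mortality stopping rule are unaffected. This is an inconsistency in safety reporting that should be corrected; it does not threaten the trial's main conclusions.

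**What to change.** 1. Reconcile Section 9.3 with Sections 4.6, 6.2 to 6.4, 9.2.1 and 9.2.2 and Appendices 1 and 2, so that one AE window and one SAE window are stated throughout.
2. In the adverse event rows of Section 6.4 and Appendix 2, and in the AE/SAE window text, exempt LVEF events as defined in 9.3, so that a qualifying result from any scan already done is recorded.
3. Tabulate separately the LVEF events found after the standard AE window and those found after transplant or non-protocol AML therapy, so that neither group is blended into the on-treatment rate.
4. Report the cardiac AE rate with its observation window, the number of patients scanned and the day of each patient's last scan.
5. Make the description of monitoring in 9.3 and the scheduled imaging agree, including whether the Day 150 scan belongs in Sections 6.2 to 6.4. Which imaging schedule applies is for the investigators to decide; the recording change needs no extra scans.

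The cost is wording in the sections named and one CRF field. The downside is that a few more cardiac events may be reported, some from scans without a common schedule.
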